3. STUDY DESIGN

The present study is a 2-week double-arm randomized controlled trial.

The study will be carried out in the following ways:

- Randomization: Using a computer-generated, centralized random number with random codes (A, B) placed in sequentially numbered sealed opaque envelopes provided by the study consultant. A simple randomization procedure will be used.
- Concealment of assignment: Doctors involved in patient treatment will never know which mouthwash will be delivered to patients. Identical and indistinguishable bottles with mouthwash will be prepared by a person designated by the sponsor. The mouthwash will be poured into identical vials labeled with only one letter (A, B), and only the person designated by the sponsor will be of which product matches the letters. The random assignment will be made by opening the sequentially numbered sealed envelope just before the surgery.
- Blinded assessment: A single, independent, blinded assessor will perform all clinical measurements. Patients will not be aware of the mouthwash they will use. In addition, the operator evaluators and statistician will remain blinded until statistical analysis (blinded study) is performed. The codices (A, B) will be broken at the time of writing the manuscript.

The principles outlined in the Declaration of Helsinki on clinical research involving human subjects will be respected. Written informed consent will be obtained for each patient.

The study will be reported according to the CONSORT statement to improve the quality of reports of randomized parallel-group trials (<http://www.consort-statement.org/>).

A total of 3 visits will therefore be carried out:

- A screening/baseline visit will help establish patients' eligibility for inclusion in the study, followed by baseline data recording and first supervised mouthwash application
- A 1-week experimental visit
- A 2-week experimental visit and end of study

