4.1 Treatment

The local trial manager will open the sequentially numbered sealed pouch corresponding to the patient's enrollment number and provide the patient with the randomly assigned coded vial (A, B) instructing the patient to rinse the ulcer with mouthwash, twice a day, after oral hygiene.

The treatments assigned are:

- Curasept Afte Rapid Mouthwash: Dicaprylyl Ether, Coco-Caprylate/Caprate, Hydrolyzed RNA/DNA, Hyaluronic Acid, Cetyl Palmitate, Beta-Glucan.

Versus

- Placebo mouthwash

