4.4 Study program

Screening and baseline visit (V1)

Potentially eligible patients are screened to determine their eligibility for the study. Complete (Patient Eligibility CRF) and record the number and reason for patients not included.

Prior to enrollment, all patients will be asked to sign an informed consent form to document that they understand the purpose of the study (including procedures, follow-up assessments, and any potential risks involved), have been given the opportunity to ask questions related to this study, and have been informed of treatment alternatives.

At the recruitment visit, the clinician should assess the presence of an oral ulcer, rule out lesions of neoplastic, infectious, or allergic origin, and remove, if present, any causative agents (such as sharp edges of teeth, fillings, crowns, dentures, or braces).

Primary Results:

- Pain intensity. It is measured using the VAS consisting of a 10 cm line [13], where 0 indicates no pain and 10 indicates severe pain.
- Size of each ulcer. A sheet of clear plastic will be applied directly to the ulcer and using a permanent waterproof marker the circumference of the ulcer will be traced and then placed on a graph paper and the number of mm² units included within the drawn area will be counted.

Secondary Results:

- Thermography
- Ulcer Severity Score (USS)

Treatment will be started on the same day with strict infection control measures.

The assessor will open the sequentially sealed envelope corresponding to the patient's recruitment number and write on the CRF the progressive number of the patient contained in the envelope and to which group (A or B) the patient will be assigned.

Patients will receive three anonymous bottles, coded with A, B containing the mouthwash and a scoop. Patients will apply mouthwash. This procedure will be performed under the supervision of the outcome measure which will provide further explanations to patients if necessary.

Participants will be asked to flush with 10mL of mouthwash twice daily ~~directly onto the ulcer~~. Patients were prevented from eating, drinking, or rinsing their mouths for at least one hour after each application.

Observation at 1 week (V2) and at 2 weeks (V3):

- Pain intensity using the VAS scale. The following outcome measures will be recorded by the blinded outcome assessor:
- Size of each ulcer using a clear plastic sheet
- Thermography/ Ulcer severity score (USS)

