6.2 Evaluation of secondary objectives

- a. Thermography [16,17,19]
- b. Ulcer severity Score (USS) [18]:

Ulcer severity Score (USS)

	Characteristics of the lesion	Score	Description of the USS
Average number of injuries			Score = average number of ulcers in a culture Maximum score = 20
Average lesion size (in mm)			Score = mean size of ulcers in mm Maximum score = 20
Average duration of lesions (in weeks)			Score = number of 1/2 weeks i.e. Half a week (3 days) scores 1, one and

			a half weeks (10 days) scores 3. Maximum score = 10
Injury-free period (in weeks)			Score = 10 minus the average ulcer-free period in weeks Maximum score = 10 (never ulcer-free)
Patient-perceived pain (scaled from 0–10)			1 for slight discomfort in the presence of ulcers. ¹⁰ for excruciating ulcers that interfere with eating and speaking Maximum score = 10
Site of injury	Group 1 Labial mucosa Buccal mucosa Buccal sulcus Soft palate Belly of the tongue Floor of the mouth Group 2 Hard palate Adherent gum Alveolar ridge Dore of tongue Tonsils Tonsil pillars Uvula Oropharynx		Score = total of sites involved 1 for each site of group 1 (non-keratinized mucosa) 2 for each site of group 2 (keratinized, specialized) Maximum score = 10
Scarring	Yes/No		USS Total

Complications and adverse events: Any post-operative complications and adverse events (mucosal irritation, allergic reactions, etc.) will be recorded and reported by study group by blinded evaluators in the Complications, protocol deviation, and drop out.

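### Every bottle carries one of two arm-wide letters, so one confirmed link between a letter and a product reveals all 60 allocations to anyone who sees the letters

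*Combined protocol and SAP*

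**What the plan says.** Section 3 (Study Design) sets up simple randomisation with "random codes (A, B) placed in sequentially numbered sealed opaque envelopes provided by the study consultant". On the product it says: "The mouthwash will be poured into identical vials labeled with only one letter (A, B". It adds three safeguards: the bottles are to look the same, only the sponsor's designee knows which product each letter stands for, and the letters are decoded when the manuscript is written. On measurement it says: "A single, independent, blinded assessor will perform all clinical measurements".

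The same two letters reach the patient and the CRF:

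- Section 4.1 has the local trial manager open the numbered pouch and "provide the patient with the randomly assigned coded vial (A, B".
- Section 4.4 says "Patients will receive three anonymous bottles, coded with A, B containing the mouthwash and a scoop".
- Section 4.4 also says "The assessor will open the sequentially sealed envelope corresponding to the patient's recruitment number", and that this person writes on the CRF "to which group (A or B) the patient will be assigned".

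Section 6.2 says that complications and adverse events, with mucosal irritation and allergic reactions as examples, "will be recorded and reported by study group by blinded evaluators".

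The sequential numbers belong to the envelopes and the patients. No number specific to a patient is described for the product, and no procedure for breaking one patient's code is described.

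**The concern.** A code shared by a whole arm has a single point of failure. Once someone who sees the letters learns for certain what A is, that person knows the allocation of every patient, including those not yet measured. A realistic route is an allergic reaction, which 6.2 anticipates, after which the product has to be identified.

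At stake are the outcomes that depend on the assessor's hand or judgement. Ulcer area, one of the two primary results in 4.4, is traced by hand on a plastic sheet. Thermography and several USS components also pass through the assessor. One person measures everyone, so knowledge gained from one patient carries to all later measurements. A leak of this kind cannot be undone once the trial is running.

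**Working it through.** **Inputs from the documents.** Two codes, A and B (Section 3). One assessor (Section 3). Three bottles per patient (4.4). Evaluable target 29 per group with 3% drop-out (7.1).

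**Number of patients.** 29 / (1 − 0.03) = 29.9, rounded up to 30 per group, as 7.1 states; 2 × 30 = 60. (Whether 29 follows from the effect size and SD in 7.1 is a separate question and does not bear on this point.)

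**Reach of one confirmed link**

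| Labelling | Allocations revealed by one link |
|---|---|
| Two arm-wide letters | 60 of 60 (the second letter follows by elimination) |
| One number per patient | 1 of 60 = 1.7% |

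This contrast needs no assumption beyond a certain link and access to the letters.

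**Who is exposed, outcome by outcome**

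- *Traced area, thermography, assessor-rated USS parts:* exposed if the assessor knows each patient's letter and what it means. Section 4.4 supplies the first condition, because the assessor opens the envelope and records the letter. Under 4.1 the local trial manager opens it instead.
- *VAS pain, the subject of the primary test in 7.3:* rated by the patient, who sees only their own letter. It is affected only if the patient learns what that letter means.
- *Measurements made before the leak:* not affected, although the allocations behind them become known.

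**Illustration only.** Suppose each patient independently carries a probability p of producing a confirmed link. This p is assumed; nothing in the documents fixes it. Then:

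- P(at least one link among 60) = 1 − (1 − p)^60
- expected share of patients enrolled after the first link = 1 − [1 − (1 − p)^60] / (60p)
- expected number unblinded under patient numbers = 60p

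| p (assumed) | P(any link), shared letters | Expected share enrolled after it | Expected number unblinded, patient numbers |
|---|---|---|---|
| 0.5% | 26% | 13% | 0.3 |
| 1% | 45% | 25% | 0.6 |
| 2% | 70% | 41% | 1.2 |

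The third column is smaller than the second because a leak can bias only what is measured after it.

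**The case against.** The other side has several good points.

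- *The safeguards lower the chance of a leak.* This stands. Bottles are required to look alike and the key is restricted, so a recognisable bottle would be a departure from the plan. The safeguards do not limit how far a leak spreads.
- *Side-effect patterns and sensory cues do not unblind the trial.* A reader might infer that irritation clustering under one letter, or a noticed taste or film, reveals the whole trial. It gives a guess, not certainty. What a patient perceives of their own product would also remain under any numbering.
- *Evaluators may not see tallies by letter.* A reader might take 6.2 to mean that they accumulate adverse events by arm. The wording is awkward and may only describe reporting under coded groups, so it is weak support.
- *Much of the assessor risk comes from the envelope.* If someone else opens it, dispenses, and keeps the letter off the assessor's forms, a leaked letter does not tell the assessor who has it. That leaves a smaller exposure: lettered bottles in view at the supervised first application, and other staff. It is therefore too strong to say that the problem is the same whoever opens the envelope.
- *One patient's code could be disclosed without telling everyone.* The sponsor's designee could tell one person and not the assessor. The documents do not show that this is impossible; they describe no procedure for it.

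What survives is the structural point: a confirmed link has trial-wide reach among those who see the letters, and nothing elsewhere in the documents limits it.

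**Conclusion.** The point holds as a weakness of design. One confirmed letter-to-product link exposes 60 of 60 allocations to those who see the letters, against 1 of 60 with patient numbers. The main risk is bias in assessor-rated outcomes measured after the link. It is largest if 4.4 is followed as written, because the assessor then holds the letter for every patient.

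Two stronger readings should be resisted. The 26%, 45% and 70% figures are not estimates of risk: they depend wholly on assumed p and on independence between patients, and they give the chance of any leak, not of biased data. Nor do the documents support saying that the pain result is compromised for all patients, since VAS is rated by patients who do not see one another's codes.

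Confidence is high on the labelling facts and lower on how much harm would follow. This is a cheap improvement, best made before enrolment.

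**What to change.** 1. **Sections 3, 4.1 and 4.4:** label bottles only with the enrolment number, using the computer-generated list already planned. No A/B letter should appear on bottles, on site CRFs or in anything opened at the site.
2. **Keep the two roles apart where possible:** the sponsor's designee fills the bottles; the study consultant, who supplies the envelopes and so presumably holds the list, applies the numbers. Then neither holds both the sequence and the product key.
3. **Section 6.2:** evaluators record complications by patient number; the statistician tabulates them under masked group labels, which keeps the statistician blind as Section 3 requires.
4. **Code breaks:** hold one sealed break per patient, and describe the procedure.
5. **Reconcile 4.1 and 4.4** on who opens the envelope and who records what it contains.

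Cost: 60 patients × 3 bottles = about 180 labels, 60 sealed code breaks, and dispensing in numerical order. Separating list and key needs some coordination between consultant and designee. Visits, endpoints, sample size and the analysis model are unchanged.

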3. CRITERIA FOR THE SELECTION OF STUDY SUBJECTS

3.1 Inclusion Criteria

Patients must meet all of the following inclusion criteria to be eligible for study enrollment:

1. Patients with at least one well-defined ulcer
2. Any patient who is at least 18 years old and able to sign an informed consent.

3.2 Exclusion Criteria

The presence of any of the following will exclude a subject from study enrollment:

1. Intolerance or allergy to the product.
2. Patients with hematologic deficiency such as anemia, iron, vitamin B12 and/or folic acid deficiency; systemic diseases such as ulcerative colitis, Crohn's disease, Behcet's syndrome in which RAS is part of their clinical presentation; alcohol consumption and smoking; history of allergy; treatment of ulcers with systemic steroids, vitamins, antibiotics, antihistamines, oral retinoids, or immunomodulatory agents within three months prior to study entry; and the use of nonsteroidal anti-inflammatory drugs or mouthwash for the treatment of ulcer prior to 72 hours of study entry.
3. Patients who are pregnant or breastfeeding.

4. Procedure

4.1 Treatment

The local trial manager will open the sequentially numbered sealed pouch corresponding to the patient's enrollment number and provide the patient with the randomly assigned coded vial (A, B) instructing the patient to rinse the ulcer with mouthwash, twice a day, after oral hygiene.

The treatments assigned are:

- Curasept Afte Rapid Mouthwash: Dicaprylyl Ether, Coco-Caprylate/Caprate, Hydrolyzed RNA/DNA, Hyaluronic Acid, Cetyl Palmitate, Beta-Glucan.

Versus

- Placebo mouthwash

4.2 Treatment compliance

Compliance will be assessed based on the information recorded at the last visit by the subject and the information recorded in the CRF during the treatment visits.

4.3 Product Storage

Store in a cool place (< 30°C) and keep away from light sources in an unopened original vial

STUDY PLAN

4.4 Study program

Screening and baseline visit (V1)

Potentially eligible patients are screened to determine their eligibility for the study. Complete (Patient Eligibility CRF) and record the number and reason for patients not included.

Prior to enrollment, all patients will be asked to sign an informed consent form to document that they understand the purpose of the study (including procedures, follow-up assessments, and any potential risks involved), have been given the opportunity to ask questions related to this study, and have been informed of treatment alternatives.

At the recruitment visit, the clinician should assess the presence of an oral ulcer, rule out lesions of neoplastic, infectious, or allergic origin, and remove, if present, any causative agents (such as sharp edges of teeth, fillings, crowns, dentures, or braces).

Primary Results:

- Pain intensity. It is measured using the VAS consisting of a 10 cm line [13], where 0 indicates no pain and 10 indicates severe pain.
- Size of each ulcer. A sheet of clear plastic will be applied directly to the ulcer and using a permanent waterproof marker the circumference of the ulcer will be traced and then placed on a graph paper and the number of mm² units included within the drawn area will be counted.

Secondary Results:

- Thermography
- Ulcer Severity Score (USS)

Treatment will be started on the same day with strict infection control measures.

The assessor will open the sequentially sealed envelope corresponding to the patient's recruitment number and write on the CRF the progressive number of the patient contained in the envelope and to which group (A or B) the patient will be assigned.

Patients will receive three anonymous bottles, coded with A, B containing the mouthwash and a scoop. Patients will apply mouthwash. This procedure will be performed under the supervision of the outcome measure which will provide further explanations to patients if necessary.

Participants will be asked to flush with 10mL of mouthwash twice daily ~~directly onto the ulcer~~. Patients were prevented from eating, drinking, or rinsing their mouths for at least one hour after each application.

Observation at 1 week (V2) and at 2 weeks (V3):

- Pain intensity using the VAS scale. The following outcome measures will be recorded by the blinded outcome assessor:
- Size of each ulcer using a clear plastic sheet
- Thermography/ Ulcer severity score (USS)

In the event of any complication observed during any of the scheduled visits or during an emergency visit, protocol deviation and drop out should be filled out CRF.

Unscheduled visits may be made during the study at the discretion of the Investigator. Relevant information will be collected in the CRF.

The study plan and the scheduled items are summarized in the following flowchart:

Visit	Screening and Baseline (V1)	1 week (V2)	2 week (V3)
	Day 0	Day 7	Day 14
Evaluation			
Inclusion and Exclusion Criteria	✓		
Informed consent	✓		
First mouthwash application	✓		
Pain Assessment (VAS)	✓	✓	✓
Ulcer measurement	✓	✓	✓
Thermography	✓	✓	✓
Ulcer severity Score (USS)	✓	✓	✓
Complications		✓	✓

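### Sections 4.1 and 4.4 name different people to open the allocation envelope, and on its natural reading 4.4 shows the outcome assessor each patient's group letter

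*Combined protocol and SAP*

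**What the plan says.** Two sections name the person who opens the allocation envelope.

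- 4.1 Treatment: "The local trial manager will open the sequentially numbered sealed pouch" for the patient's number, and the same person hands over the coded vial.
- 4.4 Study program, V1: "The assessor will open the sequentially sealed envelope", and that person writes on the CRF the patient's number and "to which group (A or B) the patient will be assigned".

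Study Design describes the step in the passive and names nobody: "The random assignment will be made by opening the sequentially numbered sealed envelope just before the surgery". It does give every clinical measurement to one independent, blinded assessor. It also says that each vial carries a single letter, A or B, that only one sponsor designee knows which product each letter stands for, and that the codes are broken when the manuscript is written.

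Section 4.4 goes on: "Patients will receive three anonymous bottles, coded with A, B containing the mouthwash and a scoop". Of the first application it says "This procedure will be performed under the supervision of the outcome measure". For V2 and V3 it says "The following outcome measures will be recorded by the blinded outcome assessor".

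Three other places bear on the letter. Section 6.2 has blinded evaluators report complications by study group. Section 6.1.2 appears to ask for the study group and the reason for each drop-out. The form list in section 8 has a consent form, an eligibility form, a rating form and a combined form for complications, deviations and drop-outs. It has no allocation log.

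**The concern.** Site staff cannot follow 4.1 and 4.4 as both are written. If they follow 4.4 and its assessor is the outcome assessor, the person who traces the ulcers also knows which patients belong together. With two fixed letters and one assessor, impressions of how A patients and B patients are healing can build up over the trial and colour later readings. One correct guess, or one code break, would then reveal the allocation of every patient whose letter is known. At stake is the masking of the outcomes that rest on the assessor's judgement, and the accuracy of the blinding statement in the CONSORT report that the plan promises.

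**Working it through.** No formula applies. The check sets the sections side by side.

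**1. Is it the same step?** Yes. Pouch and envelope, and enrolment number and recruitment number, are wording variants. Both texts open a sequential sealed packet for one patient, who then receives lettered product.

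**2. Who opens it?**

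| Section | Opener | Task attached |
|---|---|---|
| Study Design | none named | assignment |
| 4.1 Treatment | local trial manager | hands over the coded vial |
| 4.4 Study program | the assessor | writes the letter on a CRF |

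Two sections name an opener, and they name different roles.

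**3. Who is the assessor in 4.4?** The only assessor defined in the plan is the blinded one in Study Design, so that is the natural reading. It is not certain: 4.4 adds the words blinded and outcome when it turns to V2 and V3, and Study Design also mentions evaluators in the plural.

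**4. What does that person learn, and when?** The letter, at V1. Section 4.4 lists the baseline measures before the envelope is opened, so on that order baseline is not affected. For the letter to be known at Day 7 or Day 14, the assessor must remember it or see it again on a form. Section 4.4 does not say which CRF carries it.

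**5. Is there a second route?** Possibly. The supervisor of the first application is described by words that name no role. If the outcome assessor is meant, that person is present while a lettered bottle is used, and correcting the opener alone would not be enough.

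**6. Which outcomes are exposed?**

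- Exposed: ulcer area traced by hand and counted on graph paper (a listed primary result), thermography, the USS items found on examination (such as lesion number, size and site), and complications.
- Much less exposed: VAS pain, taken here as rated by the patient. The primary test in 7.3 is the VAS change from baseline at Day 7.

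**7. How far could it reach?** Section 7.1 plans 30 per group, so 2 × 30 = 60 patients. Two post-baseline visits give at most 60 × 2 = 120 assessments. This bounds the exposure; it is not an estimate of bias.

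**The case against.** The strongest reply is that a letter is not a product. The plan rests its blinding on identical bottles and a key that only the sponsor's designee holds, and 6.2 expects blinded evaluators to report by study group, which needs the letter. The plan may therefore regard knowing the letter as compatible with being blinded. This stands to the extent that a reader might infer from 4.4 that the assessor is unblinded to treatment, and the documents do not support that. It does not remove the point, because knowing who shares a letter is still information that a masked assessor should not have.

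Second, the harm depends on who the assessor in 4.4 is, and the supervision sentence is garbled. Both are true, so the harm is stated conditionally. The contradiction between 4.1 and 4.4 needs no such condition.

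Third, a reader might infer that the letter is known at both later visits. That goes too far: writing it once at V1 among 60 patients does not mean knowing it at Day 7 or Day 14.

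Fourth, nothing ranks 4.1 above 4.4. That is correct. The trial manager is preferred only because the plan gives that role no measurements.

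Finally, the exposure comes from using one letter per arm, and patients will still hold lettered bottles. A chance sight of a bottle therefore remains possible after the fix, but routine recording of the letter by the assessor would end.

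**Conclusion.** The contradiction over who opens the envelope is certain and should be corrected. The weakening of masking is conditional: it requires that 4.4 is followed, that its assessor is the outcome assessor, and, for the later visits, that the letter is remembered or appears on a form in use. Under those conditions it could touch all 60 planned patients at Day 7 and Day 14 for traced area, thermography, the examined USS items and complications. The size and direction of any bias cannot be derived from the documents, and none is claimed.

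The documents do not show that the product is disclosed, that baseline is contaminated, or that the Day 7 VAS test is undermined. This is a matter to put right before enrolment, not one that overturns the primary analysis.

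**What to change.** 1. Reconcile 4.1 and 4.4 so that one role that measures no outcomes opens the envelope and dispenses the bottles. The local trial manager named in 4.1 fits, provided the sponsor confirms that this person is not also the assessor. If the assessor in 4.4 already means someone else, name that role and bring 4.1 into line.
2. In 4.4, replace the garbled supervisor of the first application with a named role other than the outcome assessor.
3. Record the letter on an allocation log added to the form list in section 8. Keep it off the rating form and any other form the outcome assessor uses.
4. Align 6.1.2 and 6.2 so that the study group is attached to drop-outs and complications from the log, by someone other than the outcome assessor.

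The cost is rewording in 4.4, 6.1.2, 6.2 and the form list in section 8 (and in 4.1 only if another opener is chosen), plus one log. No extra staff, visits or patients are needed.

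### The assessor described as blinded is also given the envelope, the group letter and, on the natural reading, supervision of the first rinse, and the plan does not say that the placebo liquid matches the test product

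*Combined protocol and SAP*

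**What the plan says.** - **Section 3, Study design (blinded assessment):** "A single, independent, blinded assessor will perform all clinical measurements".
- **Section 3, Study design (concealment):** "Identical and indistinguishable bottles with mouthwash will be prepared by a person designated by the sponsor". The vials carry a single letter, A or B, and only the sponsor's designee holds the key. Patients are also stated to be unaware of their product. Baseline data are recorded before the supervised first application.
- **Section 4.4, Study program (V1):** "The assessor will open the sequentially sealed envelope corresponding to the" patient's recruitment number and note on the CRF "to which group (A or B) the patient will be assigned". On the first application, a few lines later: "This procedure will be performed under the supervision of the outcome measure which will provide further explanations to patients if necessary".
- **Section 4.4 (V2 and V3):** "The following outcome measures will be recorded by the blinded outcome assessor".
- **Section 4.1, Treatment:** "The local trial manager will open the sequentially numbered sealed pouch corresponding to the" patient's enrolment number. The same person then hands over the coded vial and instructs the patient.
- **Sections 2 and 4.1:** the test product is listed by ingredient. The control is named only as a placebo mouthwash, with no composition, colour, smell, taste or texture.

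**The concern.** A blinded assessor is normally kept away from allocation and from the product. Section 4.4 puts the person who makes all later measurements at the point where the letter is revealed and the liquid is first used. If the two liquids can be told apart, that person could learn which letter goes with which product. Because the code has only two letters, that knowledge would cover the whole trial. At stake is detection bias in outcomes that depend on the assessor's judgement, above all the hand-traced ulcer area, which sections 4.4 and 6.1 list as a primary outcome and section 2 includes in the null hypothesis.

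**Working it through.** The documents give no recognition rate and no estimate of assessor bias, so there is no plan figure to reproduce. The check sets the sections side by side; only the last step is arithmetic.

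**1. Who supervises the first rinse?** The sentence in section 4.4 names a measure, not a person. Whatever supervises and explains must be a person. The same section gives the envelope to the assessor just before and the V2 and V3 recordings to the blinded outcome assessor just after. The outcome assessor is the only sensible reading, though it remains a reading.

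**2. Who handles allocation?**

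| Task | Section 4.1 | Section 4.4 |
|---|---|---|
| Opens the envelope | Local trial manager | Assessor |
| Records A or B on the CRF | Not stated | Assessor |
| Hands over the product | Local trial manager | Not stated |
| Supervises and explains the first rinse | Not stated (instructs the patient) | Assessor, on the reading in step 1 |

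The first row is a plain contradiction and does not depend on the garbled sentence.

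**3. What does the masking cover?** Section 3 describes the containers and the key. No section says that the two liquids look, smell, taste or feel alike.

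**4. What would recognition reveal?** Section 7.1 plans 30 per group, so 2 × 30 = 60 patients, all measured by one assessor, under two letters with one per arm. An assessor who knows each patient's letter and recognises the product in one patient could infer the assignment of all 60.

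**5. Which outcomes are exposed?**
- *Ulcer area:* traced by hand and counted on graph paper, so exposed.
- *Thermography:* recorded by the assessor. The documents do not say how images are read, so the room for judgement is unknown.
- *USS:* the listed maxima in section 6.2 are number 20, size 20, duration 10, ulcer-free period 10, pain 10 and site 10, a total of 80. Duration, ulcer-free period and pain depend on patient report or history: 10 + 10 + 10 = 30. At most 80 − 30 = 50 points can be scored by the assessor.
- *VAS:* the patient's own rating, and the primary endpoint tested in section 7.3. The assessor could affect it only indirectly.
- *Baseline values:* recorded before the rinse, so the exposure concerns V2 and V3.

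**6. How sensitive is a tracing?** Assume a circular ulcer of diameter d mm and an outline drawn 0.25 mm too far inward all round. The diameter falls by 0.5 mm and the relative change in area is ((d − 0.5)/d)² − 1.
- d = 3: (2.5/3)² − 1 = −30.6%
- d = 4: (3.5/4)² − 1 = −23.4%
- d = 6: (5.5/6)² − 1 = −16.0%

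The shape, the diameters and the shift are assumptions, not protocol figures. The results show how strongly one tracing responds to a small drift, not how much bias to expect.

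**The case against.** The strongest reply is that being present at a rinse breaks the blind only if the liquids differ noticeably, and nothing shows that they do. Section 3 speaks of indistinguishable bottles and of patients who do not know their product. Patients use the liquid for 14 days, so that statement presupposes a liquid they cannot recognise. If it holds, an assessor who watches one rinse learns no more than they do. The oily and waxy ingredients of the test product prove no contrast, because the placebo's composition is not given. The key stays with the sponsor's designee, supervision happens once, and explanations are given only when needed.

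Most of this stands. A reader might infer that the assessor sees and smells the product and is therefore unblinded, or that three of the four efficacy outcomes lose their protection. The documents support neither. They do not mention smell, they do not show that the liquids differ, part of the USS comes from the patient, and the reading of thermography is undescribed. Nor do the tracing figures amount to a treatment difference: that would need a consistent shift in one arm and not the other, hence a belief about which product is active.

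What the reply does not remove is the conflict between sections 4.1 and 4.4, the assessor's access to the letter, and the lack of any statement that the liquids match. A claim that patients are blinded states an intention; it does not describe how the placebo achieves it.

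**Conclusion.** The point holds as a risk the plan leaves open, and it should be corrected. Section 4.4 gives tasks to the assessor that sit badly with the independence and blinding promised in section 3, and it contradicts section 4.1 on who opens the envelope. With one letter per arm and a placebo liquid that is not described, a single recognition could extend to every patient.

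The conclusion about the rinse rests on the natural reading of a garbled sentence; the conclusion about the envelope and the letter rests on plain text. Harm further requires that the liquids can be told apart, which is not established. The exposure covers ulcer area, thermography to an unknown extent, and at most 50 of the 80 listed USS points at V2 and V3. The VAS comparison in section 7.3 is affected only indirectly. The size of any bias cannot be derived from the documents.

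**What to change.** Reconcile section 3 (Study design) with sections 4.1 and 4.4 as follows.

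1. The local trial manager, confirmed not to be the outcome assessor, opens the envelope, records the letter, hands over the product and supervises and explains the first rinse. This happens after the assessor has finished the baseline measurements and left.
2. The letter is kept off every form that the assessor uses, including the rating form and the complications form.
3. Patients are asked not to describe the taste, look or feel of the product to the assessor at V2 and V3, and are told in the same instruction to report all symptoms and adverse events. Without that exception the request could discourage the adverse-event reporting required in section 6.2.
4. The protocol states whether the placebo liquid is matched to the test product in look, smell, taste and texture.

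The cost is wording and a small reallocation of tasks among roles already named in the protocol. If the trial manager and the assessor turn out to be the same person, a second person is needed for these tasks; the documents do not settle this.
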